11. ADVERSE EVENTS

No adverse effects were expected in this study, as no adverse events suspected of being related to plitidepsin in the treated patients have been reported since the APLICOV-PC study ended. However, if an adverse effect is observed that may be related to the study procedures, pharmacovigilance will be notified according to the current regulations.

12. STATISTICAL CONSIDERATIONS

12.1. General considerations

This section describes the main analyses that will be carried out. The statistical analysis plan to be approved by the sponsor will include additional information on analyses, management of unavailable data and analytical methods. All data will be analysed with the SAS statistical analysis system, version 9.4. All analyses will be carried out mainly by descriptive statistical methods. Continuous endpoints will be described using maximum, minimum, Q1 and Q3, mean, median and standard deviation. Categorical endpoints will be described with frequencies and percentages as well as the exact 95% confidence interval of the relevant study variables. All results will be presented separately by treatment arm and severity of the information upon entry into the APLICOV-PC study.

The final statistical study that will be the basis of the study's final report, will cover the total population of patients once the extension study has ended.

12.2. Sample size

The main objective of the study is to evaluate the incidence of post-COVID morbidity and characterize its profile in patients who participated in the APLICOV-PC study. Given that a total of 45 patients received plitidepsin in said study, of which 3 died as a consequence of the progression of the disease, the maximum number of patients who could participate in the study is limited to 42.

Assuming an average incidence of post-COVID complications of 15%, this study would have a power of 80% for detecting a reduction of 10%: if 3 or less patients presented post-COVID complications, the study would reject the null hypothesis (incidence of post-COVID complications: 15%) and would accept the alternative (5%), with an alpha error of 0.05 (unilateral).

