- The terminal half-life exceeding 30 hours supports a pharmacologically valid model of exposure, administering the medication over 3 consecutive days. With all the three dosage levels used (1.5 mg, 2.0 mg and 2.5 mg), plasma concentrations above IC₅₀ were obtained throughout the treatment period and remained above IC₉₀ for most of the administration interval. The accumulation after three repeated administrations is minimal.

Figure 2. Total plasma concentration profiles vs. plitidepsin time predicted for the administration schedule and doses used in the APLICOV-PC study.

The horizontal lines represent the total plasma concentrations associated with lung concentrations equivalent to IC50, IC90 and 3xIC90 *in vitro*.

The APLICOV-PC proof-of-concept study has validated the proposed hypothesis in terms of impact on viral load (Fig. 3), full recovery / discharge from hospital rapidly induced (Fig. 4) and very relevant impact on lymphocyte reconstitution and other relevant inflammatory parameters (Fig. 5).

Figure 3. Effect of Plitidepsin and Remdesivir on viral load.

[figure not shown]

Figure 4. Time until discharge from hospital by dose and category (FDA)

[figure not shown]
[figure not shown]

Figure 5. Inflammatory markers in APLICOV-PC patients: Effect of the Dose in Subjects with Moderate COVID-19 according to the FDA.

Therefore, these results generated in the APLICOV-PC proof of concept study are deemed to be compatible with consideration as a tangible post-COVID clinical benefit, in which reference is made to the prevention/minimisation of

complications related to the SARS CoV2 infection. Also, it should be highlighted that 87% of the patients had a moderate to severe illness when they entered the APLICOV-PC study and, on day 15, 82% of the patients had already been discharged.

The last patient was included in the APLICOV-PC study in November 2020. Therefore there is already an extensive margin of time for follow-up of almost 12 months, which justifies this study's approach.

The complications following SARS CoV2 infection represent a medical challenge. The evolutionary process following SARS CoV2 infection is critical in terms of the patient's quality of life, the emergence/persistence of morbidities, and social and pharmacoeconomic impact [3-5]. The potential impact of plitidepsin in controlling the sequelae arising from the SARS CoV2 infection is deemed sufficiently clinically relevant to justify the creation of this study.

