Post-COVID 19 Syndrome

SARS CoV2 infection is a systematic process that goes beyond affecting the respiratory tract. COVID-19 complications and sequelae are very varied and increasingly frequent and better documented. Post-COVID sequelae occur after a severe SARS CoV2 infection in patients who required hospitalisation admission. They are generally a consequence of structural damage to different organs by the infection itself and/or associated complications. Various studies point to the sequelae of this infection not only restricting the respiratory apparatus: sequelae have also been recorded in the cardiovascular system, in the kidneys and in the central and peripheral nervous system [6-11]. Psychiatric and psychological sequelae have also been documented [12].

In patients who present a severe COVID-19 clinical picture, the main sequelae is the development of pulmonar fibrosis. According to a recent metaanalysis, approximately 30% of patients hospitalized with pneumonia due to SARS CoV2 have presented fibrotic changes that persist for the first 12 months after discharge from the hospital [13].

It has been documented that patients with severe forms of COVID-19 presented significant heart injuries, including myocarditis related to infection, with a reduced systolic function and arrhythmias. Myocardial injury has been reported, which may be due to direct damage to the cardiomyocytes, systemic inflammation, myocardial interstitial fibrosis, and hypoxia [14]. Due to significant myocardial injuries in patients with severe clinical symptoms due to COVID-19, the morbidity and lethality of the illness could be high [15-17].

In severe cases of COVID-19, the systemic hyper-inflammatory response could cause long-term cognitive damage, such as, for example, memory loss, attention deficit, slower processing speed associated with cognitive functioning, along with diffuse neuronal loss [18]. Various types of neuropsychiatric clinical signs have also been observed, such as encephalopathy, mood swings, psychosis, neuromuscular dysfunction or demyelinating processes. These may accompany an acute viral infection, or may emerge weeks, months, or even later, post-

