infection, in recovered patients [19-21]. According to an electronic follow-up record of 236,379 patients during the first six months following COVID-19 diagnosis, neuropsychiatric complications emerge in 34% of cases, not including cephaea. The most common complications include mood and anxiety disorders and psychoses (24%), neuropathies (2,1%), ischaemic heart disease (2.8%) and dementia (0.67%) [22]. On the other hand, the most frequent neurological symptoms are cephaea and cognitive changes, described in up to 68% and 81% of patients, respectively, with some sort of neurological symptom after week 12 following acute infection [23]. Cognitive changes that are usually reported are lack of concentration, attention, or difficulty planning tasks.

The rapid drop in viral load of patients with COVID-19 infection may reduce the frequency of complications caused by the infection in the following months [24].

The WHO European Observatory on Health Systems and Policies estimates that 10% of infected patients remain symptomatic for at least 12 weeks after infection, resulting in long-term sick leave, leaving sequelae that in 0.8% even last more than a year [25]. A study in Spain, based on Social Security data, shows that COVID caused 1.2 million registered sick leaves by March 2021, and its authors indicate that nearly 100,000 people needed 12 weeks or more to recover from post-COVID sequelae. The casualties were justified by almost 50 different symptoms ranging from fever, shortness of breath, fatigue, anxiety, dizziness or memory loss.

On the other hand, data has been published from the COVERS CAN study conducted in the United Kingdom [25], which carried out serial Magnetic Resonance Imaging (MRI) scanning in a sample of 201 generally-healthy, middle-aged individuals, with COVID-19. The investigators found evidence of mild organ impairment of the heart (32%), lungs (33%), kidneys (12%), liver (10%), pancreas (17%), and spleen (6%) and reported that nearly 70% of the individuals suffered impairment in one or more organs 4 months after the initial symptoms of SARS-CoV2 infection, which was higher than age-matched healthy controls.

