5.2. Justification of the study

As previously indicated, the APLICOV-PC proof of concept study demonstrated the antiviral activity of plitidepsin in terms of reducing viral load, inducing recovery, and impact on lymphocyte reconstitution and other inflammatory parameters.

A percentage of patients, which varies between 10 and 25%, continue to show symptoms at 3 months after contracting the SARS CoV2 infection: For some of them this significantly restricts their life, requiring them to take long-term sickness leave from work, and leaving them with sequelae that may continue for more than one year.

With this study, we intend to evaluate whether the treatment with plitidepsin, by attaining a reduction in the viral load and a faster recovery of the patient, could have a relevant impact on the emergence of sequelae resulting from the SARS CoV2 infection.

5.3.Study objectives

Evaluate the incidence of post-COVID morbidity and characterise the complications profile in patients who participated in the APLICOV-PC study.

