6. STUDY DESIGN

6.1.Design

Multi-site extension study of the APLICOV-PC clinical study follow-up.

The plitidepsin doses considered in this trial include the three doses specified in the APLICOV-PC study:

- 1.5 mg of plitidepsin administered as a 1.5-hour infusion, once a day for 3 consecutive days (total dose 4.5 mg).
- 2.0 mg of plitidepsin administered as a 1.5-hour infusion, once a day for 3 consecutive days (total dose 6.0 mg).
- 2.5 mg of plitidepsin administered as a 1.5-hour infusion, once a day for 3 consecutive days (total dose 7.5 mg).

6.2.Primary endpoint

Incidence of complications related to COVID-19 infection.

Evaluation of the principal variable:

The following information will be gathered in this study:

- Readmissions to hospitals and causes, from the last visit of the APLICOV-PC study to the end of the extension study.
- Need for oxygen therapy and duration of the same, from last visit of APLICOV-PC study until the end of the extension study.
- Presence of complications (see annex 5) since last visit of APLICOV-PC study until the end of this extension study by the patient.

Also, once the informed consent has been signed, the following tests will be carried out in the following 7 days:

- Barthel Index [26], to assess the patient's degree of autonomy when performing activities of daily living.
- Evaluation of the dyspnea, according to the mMRC scale [27].
- Evaluation of functional capacity (6 minute walk test) [28].
- Physical examination, including weight, height, BSA, pulse oximetry, PAI (estimated annex 8).

- Full analysis, including inflammation markers.
- Chest X-ray, in patients diagnosed with pneumonia upon admission to hospital, which led to their participation in the APLICOV-PC study.
- Evaluation of pulmonary function, including dyspnea evaluation (mMRC and 6 minute walk test) (annexes 7 and 9) SaO₂, PAFI (direct or estimated) (annex 8), spirometry (forced vital capacity, FEV1 and FEV1/CVF) and the diffusion test.
- Electrocardiogram.
- Heart Ultrasound/MUGA, in patients that suffered a relevant cardiac event while participating in the APLICOV-PC study or in those patients for which it was clinically indicated during follow-up.
- Thus, an evaluation was made of both the ultrasound images and the results of the complementary (analytical or functional) tests necessary for interpreting the long-term evolution of the disease, from the start of the patient's participation in APLICOV-PC to the end of this study.

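### The 15% reference incidence in Protocol 12.2 is unsourced and not tied to this cohort, window or endpoint, so the rule of three or fewer cases cannot be read as an effect of plitidepsin

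*Protocol*

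**What the plan says.** Protocol 12.2 caps the sample at 42 (45 treated less 3 deaths). It then sets the null with "Assuming an average incidence of post-COVID complications of 15" per cent, and states that "this study would have a power of 80% for detecting a reduction of 10" percentage points, which takes 15% down to 5%. Three or fewer cases rejects the null at one-sided alpha 0.05. No reference accompanies the 15%.

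The background figures elsewhere in the protocol are:

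- Section 5.2 (echoed in SAP 2.2): "A percentage of patients, which varies between 10 and 25%, continue to show symptoms at 3 months after contracting the SARS CoV2 infection". Hospital status is not specified.
- Section 5.1: "10% of infected patients remain symptomatic for at least 12 weeks after infection".
- Section 5.1, for hospitalised pneumonia: "approximately 30% of patients hospitalized with pneumonia due to SARS CoV2 have presented fibrotic changes that persist for the first 12 months".
- Section 5.1: 34% with neuropsychiatric complications in the 6 months after diagnosis.

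On the cohort, 5.1 says that "87% of the patients had a moderate to severe illness when they entered the APLICOV-PC study", and puts follow-up at almost 12 months since the last inclusion. All were hospital admissions.

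On the endpoint, 6.2 records "Presence of complications (see annex 5) since last visit of APLICOV-PC study until the end of this extension study by the patient". Annex 5 lists 16 symptoms and an open item, each yes or no, with start and end dates and no minimum duration. Section 12.4 also has a count limited to complications that a physician attributes to persistent illness. SAP Table 11.1.1 shows three versions: related, related or unknown, and regardless of relationship.

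Protocol 12.1 calls the analyses mainly descriptive and promises exact 95% confidence intervals. The SAP contains neither the test against 15% nor the cutoff.

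**The concern.** In a single-arm study the reference rate takes the place of the control group. A low count says something about the drug only if the same patients, observed for the same time with the same case definition, would have had about 15% complications without it. Nothing in the documents supports that.

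The nearest figure, 10 to 25%, differs in two ways. It is not limited to hospitalised patients, and it measures persistence at one time point. The Annex 5 count accumulates events of any duration over roughly a year. Section 12.2 also does not say which of the several complication counts the rule applies to.

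Section 5.2 says the study is meant to show whether plitidepsin affects sequelae, so a reader could take the result of the 12.2 rule as the answer. Depending on the true background and on the count used, that answer could be a missed effect or a false success.

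**Working it through.** **Inputs.** From Protocol 12.2: n = 42, cutoff 3, null 15%, alternative 5%, one-sided alpha 0.05, power 80%. Background rates: 10% and 25% are the ends of the range in 5.2; 30% and 34% come from 5.1. Applying any of them to this cohort is an assumption made to show the range.

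**Formula.** The rule is met with probability P(X ≤ 3) = Σ C(42,k) p^k (1−p)^(42−k), summed over k = 0 to 3.

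**The plan's own figures.**

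- At p = 0.15, the cumulative probabilities for 0, 1, 2 and 3 cases are 0.0011, 0.0091, 0.0382 and 0.1067. The exact one-sided alpha is 0.107, not 0.05.
- At p = 0.05, P(X ≤ 3) = 0.843, so power is 84%, not 80%.
- A cutoff of 2 keeps alpha at 0.038, but power is then 0.649.
- The cutoff of 3 does match a one-sided Wald bound. For 3/42 = 0.0714, the upper limit is 0.0714 + 1.645 × √(0.0714 × 0.9286/42) = 0.137, below 0.15. For 4/42 it is 0.170, above 0.15. The exact size of that test is still 0.107.
- The exact one-sided 95% upper limit for 3/42 is 17.4%, which does not exclude 15%. The two-sided exact 95% interval is 1.5% to 19.5%.

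**Chance of meeting the rule, by true background.**

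| Background | No drug effect | Rate halved | Rate cut to one third |
|---|---|---|---|
| 10% | 38.4% | – | – |
| 15% | 10.7% | – | 84.3% |
| 17.5% | 4.9% | – | – |
| 20% | 2.1% | – | – |
| 25% | 0.30% | 21.3% | 53.2% |
| 30% | 0.034% | 10.7% | 38.4% |
| 34% | 0.005% | 5.8% | 28.4% |

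Across the protocol's own 10 to 25% range, the no-effect pass probability changes by a factor of about 127 (0.3836/0.00303). The cutoff keeps alpha at or below 0.05 only if the background is about 17.5% or more. At a 30% background, a true halving to 15% is missed with probability 1 − 0.107 = 0.893.

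**The exact cutoff moves with the reference.** At n = 42, the largest count with exact alpha at or below 0.05 is 0 for a 10% reference, 2 for 15%, 3 for 20%, 5 for 25% and 7 for 30%.

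**Participation.** 42 is a maximum, and the cutoff is not scaled to the number who consent. With 35 participants, three or fewer cases at a 15% background has probability 20.9%.

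**The case against.** The strongest reply is that little hangs on this. The objective is descriptive, N is fixed by eligibility, 12.1 calls the analyses mainly descriptive, and the SAP omits the test. That limits the consequence and makes the repair easy. The accept/reject statement is still in the protocol, and nothing there withdraws it.

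A second reply is that the higher figures fit poorly. The 30% is fibrotic change, which Annex 5 does not list. The 34% covers one domain in diagnosed patients, not specifically hospitalised ones. Both points stand, and these rates serve here only as scenarios. The alpha of 0.107 at 15% and the swing across 10 to 25% do not need them.

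Three stronger readings are tempting but not supported:

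- A reader might infer that the 15% was taken from the range in 5.2. Section 12.2 cites nothing; 15% merely lies inside that range.
- A reader might infer that a pass would be produced by the mismatch and not by the drug. If the true background is above about 17.5%, the rule is conservative. At 30%, a pass with no effect has probability 0.034%, and the harm is a missed effect.
- A reader might use the 0.8% that 5.1 gives for sequelae beyond a year to argue that success is almost guaranteed. No planned primary count is limited to such sequelae, and the figure concerns infected patients generally, with an unclear denominator.

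**Conclusion.** The point holds in this form: the 15% has no stated basis and is not matched to this cohort's severity, observation window or endpoint. The outcome of the 12.2 rule therefore cannot be interpreted as an effect, or lack of effect, of plitidepsin.

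Two results need no outside assumption about the background. At the plan's own 15%, the exact alpha is 0.107, about twice the stated 0.05. Over the protocol's own 10 to 25% range, the chance of passing with no drug effect runs from 38% to 0.3%.

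The direction of error depends on a background that the documents do not establish. If it is near 30%, as might apply to a broad count in hospitalised survivors, a true halving is missed about 89% of the time. Inflated false success, above the stated 5%, is the risk only if the background is below about 17.5%, for example under the narrower related-only count. All figures assume 42 independent participants, the maximum.

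**What to change.** In Protocol 12.2:

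- Delete the statement that three or fewer cases rejects 15% in favour of 5%, with the linked power and alpha claim.
- State that N is set by eligibility, at most 42, and that incidence will be reported with its exact 95% confidence interval as 12.1 provides, without an efficacy verdict against an external rate.

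In Protocol 12.4 and SAP section 7, name which complication count is primary among those in 12.4 and SAP Table 11.1.1.

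In SAP Tables 11.1.1 and 11.1.2:

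- Add the exact 95% interval for the primary count. The shells currently show only n (%), and SAP section 3 mentions only frequencies and percentages.
- Add two descriptive rows from the Annex 5 dates: complications ongoing at the extension visit, and complications lasting 12 weeks or more. Present neither as a matched comparison with the 10 to 25% figure; the 12-week row would include complications that began late in follow-up, which that figure does not describe.

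The cost is wording and a few derived rows. Listing 11.1.1 already carries start, end, ongoing and duration, so no new data are needed. The protocol gives up a formal efficacy verdict, which the SAP does not carry in any case.

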8.2. Replacement of subjects and reserve subjects

Not applicable. Given the characteristics of the study, those patients who do not agree to participate in the study, or who withdraw their consent, cannot be replaced.

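### The rejection rule of 3 or fewer complications in 42 patients has an exact one-sided alpha of 0.107, not 0.05, and no cut-off at n = 42 gives both alpha 0.05 and 80% power.

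*Protocol*

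**What the plan says.** Protocol section 12.2 (Sample size) starts from 45 treated patients, subtracts 3 deaths, and concludes that "the maximum number of patients who could participate in the study is limited to 42". It takes 15% as the null incidence of post-COVID complications and 5% as the alternative, and says that "this study would have a power of 80% for detecting a reduction of 10"%. The decision rule is that "if 3 or less patients presented post-COVID complications, the study would reject the null hypothesis (incidence of post-COVID complications: 15"%), "with an alpha error of 0.05 (unilateral"). It names no test or formula.

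Three other places in the protocol bear on this:

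- Section 8.2 says that "those patients who do not agree to participate in the study, or who withdraw their consent, cannot be replaced".
- Section 12.1 says that "All analyses will be carried out mainly by descriptive statistical methods", and that "Categorical endpoints will be described with frequencies and percentages as well as the exact 95% confidence interval of the relevant study variables".
- Section 5.2 gives the aim: "we intend to evaluate whether the treatment with plitidepsin, by attaining a reduction in the viral load and a faster recovery of the patient", could affect the sequelae of the infection.

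Neither Protocol section 12.4 nor the SAP (sections 3 and 7, Table 11.1.1) repeats the 15% reference, the cut-off, the alpha or the power.

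**The concern.** For a single-arm binomial rule, alpha and power follow directly from n, the cut-off and the two incidences. All four are stated, so the claim can be checked without outside information. Under the null, 42 × 0.15 = 6.3 events are expected. A count of 3 is only 3.3 below that, against a standard deviation of √(42 × 0.15 × 0.85) = 2.31, which is not far enough into the tail for a 5% error.

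The study has no control arm, and this is the only null hypothesis, alternative and rejection rule for the complication incidence in either document. A report that used it to claim a reduction would quote a 5% error rate when the real one is more than 10%.

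**Working it through.** **Inputs** (all from Protocol section 12.2): n = 42, null incidence 0.15, alternative 0.05, reject if X ≤ 3, alpha 0.05 one-sided, power 0.80.

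**Formula.** P(X ≤ c | n, p) = Σ C(n,k) p^k (1 − p)^(n−k), for k = 0 to c. At p = 0.15 this is alpha; at p = 0.05 it is power.

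**The plan's own rule, c = 3, n = 42**

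- Alpha: 0.0011 + 0.0080 + 0.0291 + 0.0685 = **0.1067** (stated 0.05).
- Power: 0.1160 + 0.2564 + 0.2766 + 0.1941 = **0.8431** (stated 0.80, so met).

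**All relevant cut-offs at n = 42**

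| Reject if X ≤ | alpha (p = 0.15) | power (p = 0.05) |
|---|---|---|
| 1 | 0.0091 | 0.3724 |
| 2 | 0.0382 | 0.6490 |
| 3 | 0.1067 | 0.8431 |
| 4 | 0.2245 | 0.9427 |

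Alpha at or below 0.05 needs c ≤ 2; power of at least 0.80 needs c ≥ 3. No integer satisfies both. The smallest n that meets both targets exactly is 59, with c = 4 (alpha 0.0469, power 0.828).

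**Other ways the stated figures might have arisen**

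- All 45 treated patients, c = 3: alpha 0.0785, power 0.813.
- Normal approximation with null variance: z = (3/42 − 0.15)/√(0.15 × 0.85/42) = −1.43, one-sided p = 0.077. With continuity correction, p = 0.113.
- Mid-p: 0.073. Poisson: 0.126.
- Wald test with variance at the observed rate: p = 0.024 for 3/42. This nominally rejects, but the probability that the rule rejects a true 15% incidence is still 0.107.
- A 10% reduction read as relative (15% to 13.5%) contradicts the stated 5% alternative and gives power of only 16.3%.
- The normal-approximation formula at one-sided alpha 0.10 needs n = 41.1 and gives power 0.809 at n = 42. The design may have been calculated at 0.10 and labelled 0.05, but the documents do not show this.

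**Cross-check by exact (Clopper-Pearson) limits.** The one-sided 95% upper limit is 17.4% for 3/42, which does not exclude 15%, and 14.2% for 2/42, which does. The two-sided 95% upper limit for 3/42 is 19.5%, so at three events the rule would reject 15% while the interval promised in section 12.1 would contain it.

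**Fewer than 42 patients.** The documents give no participation rate, so the values of n below are an assumed range.

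| n analysed | alpha if 3 is kept | largest c with alpha ≤ 0.05 | power at that c |
|---|---|---|---|
| 42 | 0.107 | 2 | 0.649 |
| 40 | 0.130 | 2 | 0.677 |
| 38 | 0.158 | 1 | 0.427 |
| 35 | 0.209 | 1 | 0.472 |
| 30 | 0.322 | 1 | 0.554 |

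The largest valid cut-off is 2 for n = 40 to 42 and 1 for n = 30 to 39. With c = 1, power is lowest at n = 39 (0.413). A count of 3 first holds alpha at or below 0.05 at n = 50 (alpha 0.046, power 0.760).

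**The case against.** The strongest objection is that nothing planned depends on this sentence. The sample size was not derived from it: 42 is simply the number of survivors. The analyses are described as mainly descriptive, and no analysis section or table shell contains a null value or a cut-off. Correcting or deleting the sentence would change no planned output. That is true, and it limits the impact. It does not make the sentence right. The protocol still says what the study would reject and accept, section 5.2 states an aim of judging whether treatment affects sequelae, and nothing else in the documents corrects the figure.

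A second objection is that the documents do not show which figure is the mistake. If 3 should have read 2, alpha holds and the cut-off and power are wrong. This is fair: what is established is that cut-off, alpha and power are mutually inconsistent. As written, the rule delivers its power and misses its alpha.

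Third, the protocol never says that 3 would be kept with fewer than 42 patients. That also stands, so the results for smaller n show sensitivity only; the error at n = 42 does not depend on them.

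Finally, any restated rule needs a defined count. SAP Table 11.1.1 has three complication rows, differing by relationship to the disease, and section 12.2 does not say which one the rule uses. The fix has to settle this.

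**Conclusion.** The point holds. At n = 42 the stated rule has an exact one-sided alpha of 0.107, about twice the stated 0.05, with power 84%. Holding alpha at or below 0.05 means a cut-off of 2 and power of 65%. No cut-off at 42, nor the same cut-off applied to all 45 treated patients, delivers what section 12.2 claims. The result assumes only independent patients with a common incidence, and takes the protocol's 15% and 5% as given.

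This should be fixed, but it does not undermine the descriptive results. The damage would come from a report that invoked the rule to claim a reduction at the 5% level.

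**What to change.** Choose one of two routes for Protocol section 12.2.

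1. **Keep a test.** Retain the cohort and the 0.05 alpha. Reject if X ≤ c, where c is the largest integer with P(X ≤ c | n analysed, 0.15) ≤ 0.05: c = 2 for 40 to 42 patients and c = 1 for 30 to 39. State the true figures at n = 42 (alpha 0.038, power 65%), and name the row of SAP Table 11.1.1 that supplies X.
2. **Treat the study as purely descriptive.** Withdraw the rule, the alpha and the power. This fits the SAP as it stands.

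Under either route, add to the Total column of SAP Table 11.1.1 the exact 95% interval promised in Protocol section 12.1. If the test is kept, add the one-sided 95% upper limit and say that the test is read from it. The two-sided 95% interval corresponds to one-sided 0.025 and contains 15% even at 2/42 (0.6% to 16.2%).

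Record the date of the change relative to review of the outcome data. Inclusion was due to end in December 2021 (Protocol section 1.14) and the SAP changes are dated 17 November 2022 (SAP section 15), so the counts may already have been known. If they were, label the restated rule post hoc.

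The cost is one paragraph in section 12.2 and an addition to one table, with no extra patients or procedures. The price of keeping the test is that the stated power falls from 80% to 65% at n = 42, and to between 41% and 55% with 30 to 39 patients.

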5.1 Definition of the study population to be analyzed

All patients who sign an informed consent form and agree to undergo the set of clinical examinations, imaging and laboratory tests specified in section 10 of the protocol, will be analyzed in order to fulfil the objectives of the study.

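### The reject/accept rule in Protocol 12.2 is a fixed count that is not tied to the number of patients analysed, so its false-positive rate rises as participation falls below 42

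*Protocol*

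**What the plan says.** Protocol 12.2 (Sample size) assumes a 15% incidence of complications, sets 5% as the alternative, and claims 80% power at a one-sided alpha of 0.05. The rule is: "if 3 or less patients presented post-COVID complications, the study would reject the null hypothesis". No number of patients is attached to that count. The same section says that "the maximum number of patients who could participate in the study is limited to 42", which is the 45 treated patients less 3 deaths.

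Three other provisions decide how many patients are analysed:

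- Protocol 8.2: "those patients who do not agree to participate in the study, or who withdraw their consent, cannot be replaced".
- SAP 5.1, matching Protocol 12.3, defines the analysed patients as "All patients who sign an informed consent form and agree to undergo the set of clinical examinations, imaging and laboratory tests".
- SAP 4 states that there is no method for missing data.

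Neither document gives a minimum number, an expected participation rate, or a cut-off for fewer than 42.

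On analysis, Protocol 12.1 calls the methods mainly descriptive and provides for exact 95% confidence intervals for relevant categorical variables. Protocol 12.4 and SAP 7 plan numbers and percentages for the primary endpoint, with no test against 15% and no cut-off. SAP 3 computes percentages on valid data.

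**The concern.** A cut-off for a binomial count is calibrated to one sample size. Here the count is fixed while the sample size can only fall: reaching 42 requires every survivor to consent, almost 12 months after the last patient entered APLICOV-PC. Each survivor who does not take part can lower the number of complications counted and can never raise it, and the cut-off stays at 3. For this rule, an absent patient has the same effect as a patient without complications.

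The error therefore goes in one direction, towards rejecting 15% and accepting 5%. The stated aim (Protocol 5.2, SAP 2.2) is to see whether plitidepsin has an impact on sequelae. A rule written in advance, with an alpha and a power, could later be cited as a prespecified criterion that was met when low attendance had helped to meet it. The observed proportion need not even be below the null value: 3 of 20 is 15.0% and 3 of 19 is 15.8%, and both satisfy the count.

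**Working it through.** **Inputs.** From Protocol 12.2: null incidence 0.15, alternative 0.05, one-sided alpha 0.05, power 0.80, reject if X ≤ 3, N at most 42. The documents give no figure for participation, so N from 18 to 42 is shown as an assumed range.

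**Formula.** P(X ≤ c | N, p) = Σ (k = 0 to c) C(N,k) p^k (1−p)^(N−k).

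**Step 1: the plan's own figures at N=42.**

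- Under p=0.15 the cumulative probabilities for c = 0, 1, 2, 3 are 0.0011, 0.0091, 0.0382 and 0.1067. The rule X ≤ 3 has alpha 0.107, not 0.05.
- Under p=0.05, P(X ≤ 3) = 0.843, against the stated 0.80.

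The stated pair is not reproduced. No N from 15 to 55 gives alpha ≤ 0.05 together with power ≥ 0.80 under X ≤ 3.

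**Step 2: the same count with fewer patients, p=0.15.**

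| N analysed | share of 42 | P(X ≤ 3) | P(X ≤ 2) |
|---|---|---|---|
| 42 | 100% | 0.107 | 0.038 |
| 40 | 95% | 0.130 | 0.049 |
| 39 | 93% | 0.143 | 0.055 |
| 38 | 90% | 0.158 | 0.062 |
| 34 | 81% | 0.228 | 0.097 |
| 30 | 71% | 0.322 | 0.151 |
| 24 | 57% | 0.505 | 0.280 |

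The last column separates this point from the alpha error at N=42. Lowering the fixed count to 2 restores alpha at 42, but three absent patients already take it above 0.05.

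**Step 3: a rule that uses N.** Let U(x,N) be the one-sided 95% Clopper-Pearson upper limit, the 0.95 quantile of Beta(x+1, N−x). Reject 15% only if U < 0.15. For x=3, U is 17.4% at N=42, 21.3% at 34 and 29.2% at 24, so three events never exclude 15% in this study. For x=2, U is 14.9% at N=40 and 15.3% at N=39, so the cut-off drops between those two.

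| N analysed | reject if | alpha at 15% | power at 5% |
|---|---|---|---|
| 40 to 42 | 2 or fewer | 0.049 to 0.038 | 68% to 65% |
| 30 to 39 | 1 or fewer | 0.048 to 0.014 | 55% to 41% |
| 19 to 29 | 0 | 0.046 to 0.009 | 38% to 23% |
| 18 or fewer | never | – | – |

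At N=18, zero events has probability 0.0536 under 15%, which is above 0.05, so no rejection region exists.

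**Step 4: dependence on who attends.** Step 2 treats the analysed patients as a random subset of the survivors. If every survivor with complications attended and only complication-free survivors stayed away, the count would be the same as with all 42 present and the false-positive rate would stay at 0.107 for any N. If those with complications were the ones less likely to attend, the rates would exceed those in the table.

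**The case against.** The strongest reply is that the count was meant for 42. That is the only participant number in 12.2, and the rule follows it directly, in the conditional, under a sample-size heading. This stands as a reading of where the 3 came from. It does not say what applies when fewer than 42 are analysed, and the section itself calls 42 a maximum.

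The second reply is that no planned analysis uses the rule. Protocol 12.4 and SAP 7 give numbers and percentages, SAP 3 uses valid-data denominators, and Protocol 12.1 provides exact intervals, so a reader would see 3/20 as 15.0% with a wide interval. This also stands, and it limits the reach of the point. A reader might infer that the trial will declare success on three or fewer events whatever the attendance; the documents do not support that, because no success declaration is carried into the analysis sections. Nor is it the only inferential element: SAP 7 screens covariates at p < 0.10 for a multivariate analysis, and SAP Table 11.13 reports Wald tests and odds-ratio limits.

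Third, low participation is hypothetical. A reader might take the figure at N=24 as a forecast that the rule will misfire more often than not. It is not one: it needs 57% participation or less, the documents give no rate, and it assumes attendance unrelated to outcome. What needs no such scenario is the excess at N=42 (0.107 against 0.05) and the absence of any link between cut-off and N.

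**Conclusion.** The point holds as a defect in the wording of Protocol 12.2. The cut-off is a fixed count, the number analysed can only be 42 or fewer, and nothing adjusts the one to the other. If the count is applied as written, the false-positive rate is 0.107 at full participation, about 0.16 with four patients absent, 0.23 with eight absent and 0.32 with twelve absent. These figures rest on the plan's own 15% null, on binomial counts, on an assumed N, and on participation being independent of complications. The possible effect of absence is always in the direction that favours the drug; its size depends on who stays away.

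The defect is related to the misstated alpha at N=42 but is not removed by moving to another fixed count. A rule based on the number analysed corrects both. Because the rule is confined to the sample-size section, this should be corrected but does not undermine the descriptive analyses.

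**What to change.** **Preferred if a test is wanted.** In Protocol 12.2, replace the fixed count with: reject 15% only if the one-sided 95% exact (Clopper-Pearson) upper limit for x/N, with N the number analysed, is below 15%. State the resulting cut-offs and power at 5%: N=40–42, 2 or fewer (68% to 65%); N=30–39, 1 or fewer (55% to 41%); N=19–29, none (38% to 23%); N=18 or fewer, rejection not possible. Withdraw the 80% power claim, and carry the same rule into SAP 7.

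**Alternative if no test is wanted.** Delete the rule with its alpha and power from 12.2. Report x/N with the exact 95% interval that Protocol 12.1 already provides for, and add that interval to SAP 7, which does not mention it.

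**Cost.** Wording in two places; no extra patients or data. The first option makes visible that power is at best 68% and falls sharply with lower participation. The second gives up a formal conclusion against 15%.
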